1 PROTOCOL SUMMARY

- Title:** The use of Melatonin in children with Neuro-developmental Disorders and impaired Sleep; a randomised, double-blind, placebo-controlled, parallel study.
- Phase:** II
- Population:** 114 children aged 3 years to 15 years 9 months, at randomisation, with a diagnosis of a neuro-developmental disorder in conjunction with a minimum six month history of impaired sleep as defined by not falling asleep within one hour of 'lights off' or 'snuggling down to sleep' at age-appropriate times for the child in 3 nights out of 5, and/or less than 6 hours of continuous sleep in 3 nights out of 5.
- Number of Sites:** Twenty five sites throughout England; see Appendix A for full details.
- Study Duration:** Potential participants will be screened and initially registered on study at T-4 Weeks. The family will be given a standardised booklet on basic sleep hygiene but no other intervention (behavioural, pharmacological or homeopathic) to try and improve their child's sleep. Sleep diaries and an actigraph will be provided with instructions for use and will be used for the duration of the 4 week sleep hygiene intervention. Contact will be re-initiated at T-2 weeks to check the sleep diaries and the actigraphy data and to stress the importance of a consistent bedtime. At the end of 4 weeks (T0), assuming the child continues to fulfil the entry criteria and further consent is provided; the child will be randomised into the study. Each child will be followed up for 12 weeks from date of randomisation, by a combination of home visits, telephone contact and clinic attendance.
- Description of Intervention:** The active compound (melatonin) and placebo (matching in package and appearance) will be administered 45 minutes prior to the child's usual bedtime; wherever possible, this time will remain the same throughout the study. The starting dose will be 0.5 mg and will increase every 7 days through 2mg and 6 mg up to a maximum of 12 mg, depending upon the patient's response to the preceding dose. The study treatment will be administered orally or, if the patient is not able to feed orally, through a nasogastric feeding tube or gastrostomy feeding tube; in these latter two situations the capsule will be opened and the study treatment suspended in an appropriate vehicle for administration.

Primary Outcome:

Total night-time sleep calculated using sleep diaries

[figure not shown]
Secondary Outcomes:

1. Total night time sleep calculated using actigraphy data
2. Sleep onset latency (the time taken to fall asleep) calculated using actigraphy data
3. Sleep onset latency (the time taken to fall asleep) calculated using sleep diaries
4. Assessment of effects on (a) cognitive function; (b) behavioural problems; (c) epilepsy; (d) quality of life; (e) sleep efficiency and behaviour (f) salivary melatonin

concentrations and (g) association of genetic variants with abnormal melatonin production.

5. Adverse effects

Protocol Summary – continued
Fig 1. Schematic of Study Design:

2 BACKGROUND INFORMATION

2.1 Introduction

Melatonin (N-acetyl-5-methoxytryptamine) is a natural substance produced by the pineal gland and is responsible for circadian rhythm producing sleep. Production of melatonin is increased in the evening and suppressed by light, making melatonin a hormonal signal of darkness. In mammals (including humans), melatonin regulates the circadian rhythm (including sleep-wake cycling). Considerable work undertaken in healthy adult volunteers has evaluated the pharmacology and pharmacokinetics of both endogenous and prescribed exogenous melatonin. Early results (subsequently confirmed) suggested that melatonin is of value in treating sleep disturbances in blind or severely visually-impaired people in whom endogenous melatonin secretion may be altered or deficient. Melatonin has also been suggested to be useful in inducing sleep in groups at specific risk of insomnia including shift-workers⁽¹⁾ and those with jet lag⁽²⁾.

Children with neurological and/or developmental disorders have a higher prevalence of sleep disturbances that are frequently chronic and are usually far more difficult to treat than their 'normally' developing peers⁽³⁻⁵⁾. These sleep disorders may result in additional learning and behaviour problems. In addition, disturbed sleep, and specifically discontinuous sleep with frequent awakenings throughout the night, commonly results in disturbed sleep in their parents and siblings with secondary detrimental effects on the family – physically, emotionally and socially – and if chronic, even on their ability to continue in employment or further education. Finally, chronic sleep disturbance of multiply disabled children are a frequent cause of families giving up their care.

Behavioural approaches used in improving sleep are difficult to apply, time-consuming and usually require skilled and scarce manpower. Treatment with commonly-used hypnotic sedative drugs is often ineffective and can result in both side effects and tolerance, and may even be contraindicated in certain situations. There is considerable evidence that chronic sleep-wake disorders of children with neuro-developmental disorders are associated with an inability to synchronise their sleep-wake cycle generating system with environmental zeitgebers, resulting in abnormal melatonin secretion⁽⁶⁻⁸⁾. Following early results suggesting that melatonin may be effective in improving sleep in these children^(3;8), together with the observation that melatonin appeared to have neither short- nor long-term side-effects, melatonin was (and continues to be) increasingly used in open studies in the treatment of sleep disorders of children with a range of neurological disabilities and disorders. Furthermore, in view of the fact that children with a range of neuro-developmental disorders will be seen by many different disciplines and specialists including general (hospital and community-based) paediatricians, paediatric neurologists and child and adolescent psychiatrists, there has been a predictable enthusiasm to find an intervention or drug that is both effective and 'safe' in treating the sleep impairment that is typically seen in these children. This would, at least in part, explain the dramatic increase in the prescription of melatonin for this population throughout the UK.

2.2 Rationale

Several studies have suggested that melatonin is beneficial in children with developmental delay and in particular those with visual problems^(3;9-11) but also in more specific neuro-genetic syndromes, including Rett syndrome⁽¹²⁾ and tuberous sclerosis⁽¹³⁾. Importantly, melatonin appears to be effective in both reducing the time it takes children to fall asleep (time to sleep onset or sleep latency) as well as increasing the total duration of continuous sleep throughout the night^(3;10;14;15). However, all of these studies have been non-randomised and anecdotal. Limited controlled clinical trial data have suggested that melatonin may significantly reduce the time to fall asleep (i.e.: reduced sleep latency) with a definite (but

statistically non-significant) increase in total sleep duration⁽¹⁶⁻¹⁹⁾. Recent placebo-controlled trials have demonstrated that melatonin appears to be effective in elementary (primary) school children without neuro-developmental delay or neurological disorders and idiopathic chronic sleep onset insomnia^(18;19) as well as in some children with epilepsy^(20;21). The drug has also been used with some success in inducing sleep in children undergoing a range of medical procedures, including sedation electroencephalograms (EEGs) and even brain scans^(22;23)

Melatonin levels in both saliva and blood vary from person to person for a number of reasons, some known, some unknown; these may include the person's age and any underlying neurological or visual impairment. Consequently, neither therapeutic levels nor physiological, nor pharmacological doses have been established. There is some evidence that there may be a dose-response relationship for both melatonin⁽²⁴⁻²⁶⁾ and melatonin agonists (β -Methyl-6-Chlormelatonin)⁽²⁷⁾. Finally, there is no convincing evidence that tolerance develops to exogenous melatonin^(9;11) and there is considerable anecdotal evidence, from practising clinicians that, in many children, once their sleep pattern has 'improved' the melatonin can even be discontinued without a relapse in the sleep disturbance.

Melatonin is considered to be a safe drug with no reported serious adverse side-effects; hypothermia, asymptomatic hypotension, drowsiness, a 'hung-over' effect and occasional headaches have been inconsistently reported from a number of anecdotal studies. One study has suggested that seizure control may deteriorate in some children with epilepsy⁽²⁸⁾ but this observation has not been confirmed in subsequent anecdotal and limited randomised controlled studies^(11;20;21); there is some anecdotal evidence that seizure control may actually improve as a secondary effect of improved sleep and increased seizure-threshold⁽³⁾.

The drug is unlicensed for this clinical use (of improving sleep in children whether or not the child has neuro-developmental problems) and it is estimated that in the UK there are currently well in excess of 5000 children being treated with melatonin. In some countries, including the USA, melatonin is considered to be a food supplement and not subject to the regulations governing medicinal agents. Finally, there are at least 50 preparations that are either being imported into, or manufactured within, the UK, including immediate release capsules and tablets, sustained-release capsules and tablets and at least one liquid formulation. The majority of these formulations are health foods/ dietary supplements with no guarantee of quality or preparations manufactured to the standards of Good Manufacturing Practice (GMP).

Current, and predominantly anecdotal evidence, together with the rapidly increasing and largely haphazard use of melatonin, clearly justifies the need to undertake a multi-centre, randomised, placebo-controlled parallel study of melatonin in children with a range of neuro-developmental delay / neurological disorders and impaired sleep to confirm (or refute) the findings that the drug may reduce the time taken to fall asleep and increase the total duration of night-time sleep.

2.3 Objective

The objective of this trial is to confirm (or refute) that immediate release melatonin is beneficial compared to placebo in improving total duration of night-time sleep in children with neuro-developmental problems.

At randomisation, each patient will be allocated their own 'individual patient package' (stored in pharmacy and dispensed according to Section 7.4) containing either melatonin or placebo. Each child will be given the first dose and kept on that dose for a minimum of seven days. For the next three weeks and at each one-week interval during this time, the child's sleep disorder will be reviewed and the medication either left unchanged or increased to the next

dose increment. There are a maximum of 3 dose increments after the starting dose of 0.5 mg, through 2, 6 and up to a maximum of 12 mg (Section 7.9). Each child will remain on whichever dose is felt to have been the most effective.

2.4 Potential Risks and Benefits

2.4.1 Potential Risks

Clinical studies in humans (adult volunteers and patients of both sexes and all ages) have not shown any consistent or serious short or long-term adverse side-effects⁽²⁹⁾. Most of the reported adverse side-effects have been described in very small numbers of patients^(16;30). Although the chronic use of exogenous melatonin for sleep problems in paediatrics appears widespread, there is a paucity of data on its safety. Melatonin is widely distributed at different densities throughout the body and appears to be implicated in various physiological functions other than sleep. There are therefore theoretical risks in the chronic administration of exogenous melatonin in this patient population. The most significant theoretical risks in this population are:

- sexual development
- nocturnal asthma
- growth
- seizures.

With age, nocturnal melatonin levels appear to decrease with the most striking falls appearing to occur around puberty. Nocturnal melatonin levels have been assessed in children at various pubertal stages and it is observed that they are higher in the earlier than in the later stages⁽³¹⁾. Whether this is cause or effect is not known but there is a potential risk that exogenous melatonin may delay sexual maturity.

Elevated endogenous melatonin levels have been associated with an increased incidence of nocturnal asthma⁽³²⁾ although there is at least one study in adults that demonstrated an improvement in sleep in adults with asthma following administration of 3mg melatonin with no apparent worsening of their asthma symptoms⁽³³⁾.

Melatonin has been observed to have a direct effect on growth hormone⁽³⁴⁾. Eight male volunteers received single doses of 0.05, 0.5 and 5mg melatonin or placebo with serum growth hormone levels measured for up to 150 minutes afterwards. Compared with placebo, growth hormone levels were found to increase for doses of 0.5 and 5mg. The exact mechanism is not clear and the effect of increases in growth hormone of this magnitude on longitudinal bone growth in children is not known.

One study has suggested that seizure control may deteriorate in some children with epilepsy⁽²⁸⁾ but this observation has not been confirmed in subsequent anecdotal and limited randomised controlled studies^(20;35); there is some anecdotal evidence that seizure control may actually improve as a secondary effect of improved sleep and increased seizure-threshold⁽³⁾. There have been two spontaneous reports to the MHRA of seizures associated with exogenous melatonin and responders to the survey by Waldron et al⁽³⁰⁾ reported an increase in seizure activity or new onset seizures.

Melatonin oral capsules contain melatonin, lactose, and magnesium stearate. Placebo oral capsules contain lactose and magnesium stearate. Individuals with lactose intolerance are able to consume significant quantities of dairy products without displaying any symptoms of lactose malabsorption, therefore individuals with lactose intolerance will be eligible for inclusion.

2.4.2 Known Potential Benefits

Very few meta-analyses^(16;29) of randomised controlled trials (RCT) exist, those that have been undertaken indicate that exogenous melatonin may improve sleep in a number of clinical situations including:

- children with neurological and psychiatric disorders
- patients with visual impairment (particularly where the visual impairment is due to an abnormality within the anterior visual pathway [specifically in patients with microphthalmia or anophthalmia] rather than in cortical visual impairment)
- elderly patients with insomnia.

Reported benefits include a reduced sleep latency time (ie: reduced time to fall asleep), reduced number of awakenings throughout the night (ie: increased periods of continuous, un-interrupted sleep throughout the night) and improved behaviour and performance during the day.

However, the reported studies have marked heterogeneity of inclusion and exclusion criteria, the type and causes of impaired sleep in the populations studied, the doses and formulations of melatonin used, methods of assessment, and reported outcomes.

3 SELECTION OF CENTRES/CLINICIANS

Each participating Centre (and investigator) has been identified on the basis of:

- being responsible for a large population of children with neuro-developmental problems
- having at least one lead clinician with a specific interest in, and responsibility for, supervising and managing children with a wide range of neuro-developmental and neurological disorders
- having had experience with prescribing melatonin
- showing enthusiasm to participate in the study
- ensuring that sufficient time, staff and adequate facilities are available for the trial
- providing information to all supporting staff members involved with the trial or with other elements of the patient's management
- identifying that they will be able to recruit a specified target number of patients (see section 9)
- acknowledging and agreeing to conform to the administrative and ethical requirements and responsibilities of the study, including signing-up to Good Clinical Practice and other regulatory documentation.

3.1 Centre/Clinician Inclusion Criteria

- a. Positive Site Specific Assessment by LREC
- b. Local R&D approval
- c. Receipt of evidence of completion of (a) and (b) by MCRN CTU
- d. Completion and return of 'Signature and Delegation Log' to MCRN CTU
- e. A speciality interest in, and clinical responsibility for, caring for children and young people with neuro-disability and neurological or neuro-developmental disorders.

3.2 Centre/Clinician Exclusion Criteria

- a. Not meeting the inclusion criteria listed above.

4 TRIAL DESIGN

4.1 Primary Outcome

1. Total duration of night-time sleep calculated using the sleep diary.

4.2 Secondary Outcomes

1. Total night time sleep calculated using actigraphy data
2. Sleep efficiency calculated from the actigraphy by (number of minutes spent sleeping in bed/total number of minutes spent in bed) x 100
3. Sleep onset latency (the time taken to fall asleep) calculated using actigraphy
4. Sleep onset latency (the time taken to fall asleep) calculated using sleep diaries
5. Composite sleep disturbance index scores
6. Daily global measure of parental perception of child's sleep quality
7. Behavioural problems assessed using Aberrant Behaviour Checklist (ABC)
8. Quality of Life of the care-giver assessed using the Family Impact Module of the PedsQL™
9. Level of daytime sleepiness of caregiver assessed using the Epworth Sleepiness Scale
10. Number and severity of seizures evaluated using seizure diaries throughout trial follow-up
11. Adverse effects of melatonin treatment assessed weekly between weeks T0W to T12W using 'TESS' (Treatment Emergent Signs and Symptoms) (Section 8.4.1)
12. Salivary melatonin concentrations
13. Associations between genetic variants and abnormal melatonin production

5 STUDY POPULATION

5.1 Inclusion Criteria

1. Children aged 3 years to 15 years 8 months at screening.
2. Diagnosis of a neuro-developmental disorder that has been made by a community paediatrician, paediatric neurologist or paediatric neurodisability consultant, categorised as:
 - a. developmental delay alone
 - b. developmental delay and epilepsy*
 - c. developmental delay and autistic spectrum disorder* (ASD)
 - d. developmental delay with 'other' ('other' is defined as the child having a specific genetic/chromosomal disorder).or any combination of the above.
3. Adaptive Behaviour Assessment System (ABAS) questionnaire score with a percentile rank below 7.
4. Minimum 5 months history of impaired sleep at screening as defined by:
 - a. not falling asleep within one hour of 'lights off' or 'snuggling down to sleep' at age-appropriate times for the child**, and/or:
 - b. less than 6 hours of continuous sleep in three nights out of five
5. Children whose parents are likely to be able to use the actigraph and complete sleep diaries
6. Children who are able to comply with taking the study drug
7. English speaking
8. Children whose parents have completed sleep diaries for an average of 5 out of 7 nights at T0W.

* In coding the presence of epilepsy and ASD diagnoses, we will require sight of documentation from relevant services that demonstrate appropriate diagnostic assessments and investigations have been used

** This will be the child's usual bedtime (recorded in the sleep diary) based upon the family's normal routine

5.2 Exclusion Criteria

1. Children treated with melatonin within 5 months prior to screening
2. Children who have been taking the following medication for less than 2 months:
 - any benzodiazepines
 - amisulpride (Solian)
 - chlorpromazine (Largactil)
 - haloperidol (Haldol)
 - olanzapine (Zyprexa)
 - risperidone (Risperdal)
 - sertindole (Serdolect)
 - sulphiride (Sulpidil, Sulpor)
 - thioridazine (Melleril)
 - trifluoperazine (Stelazine)
3. Current use of beta blockers (minimum of 7 days washout required)
4. Current use of sedative or hypnotic drugs, including Choral hydrate, Triclofos, and alimemazine tartrate (Vallergan) (minimum of 14 days washout required)
5. Children with a known allergy to melatonin
6. Regular consumption of alcohol (> 3 times per week)
7. Children for whom there are suggestive symptoms of Obstructive Sleep Apnoea Syndrome (OSAS) (such as combinations of snoring, gasping, excessive sweating or

stopping breathing during sleep), physical signs supportive of OSAS (such as very large tonsils/very small chin), or results of investigations suggesting OSAS (such as overnight pulse oximetry or polysomnography) for which the child should be referred to appropriate respiratory or ENT colleagues for specific assessment and treatment

8. Girls or young women who are pregnant at the time of screening (T– 4W)
9. Currently participating in a conflicting clinical study or participation in a clinical study involving a medicinal product within the last 3 months

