6 ENROLMENT AND RANDOMISATION

6.1 Screening

A log of potential patients will be kept, including individuals who decide not to participate in the study prior to the T-4W clinic visit and inappropriate referrals from community Paediatricians.

Screening will be performed of a patient's possible eligibility for the study and must be documented on the eCRF at the T-4W clinic visit.

Screening at T-4W (See section 8 for T-4W assessments)

1. Fully informed written proxy consent (and assent, where appropriate) to participate in sleep hygiene intervention.
2. Developmental delay indicated and tested by referrer
3. Documentation of attendance at a special school where applicable
4. ABAS questionnaire score with a percentile rank below 7
5. Documentation of previous/current history of melatonin use
6. History of sleep problems (as described in section 5.1)
7. Pregnancy test for sexually active pubertal females who have consented to this procedure.
8. Electronic submission of T-4W eCRF to MCRN CTU within 24 hours of registration.
9. Forward copy of consent/assent forms to MCRN CTU within 7 days of registration.

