6.2 Enrolment/ Baseline

Screening at T0W (See section 8 for T0W assessments)

1. A check of compliance with sleep diary and actigraphy; a minimum of 5 out of every 7 days completed
2. Review of severity of sleep problems (as described in section 5.1)
3. A check that they have not been prescribed melatonin since screening
4. Verification that eligibility criteria continue to be fulfilled.

Randomisation Process:

1. Fully informed written proxy consent (and assent, where appropriate)
2. Completion of randomisation eCRF and trial prescription
3. Attend local pharmacy department (see Table 1 for pharmacy contact details)
4. Randomisation and issue of allocated treatment by pharmacy department
5. See section 8 for T0W assessments
6. Electronic submission of T0W eCRF and allocation notification to MCRN CTU within 24 hours of randomisation by the RP
7. Forward copy of consent/assent forms to MCRN CTU within 7 days of randomisation.

Table 1. Pharmacy Contact Details

If any queries about randomisation procedure contact: Trial Co-ordinator, [name] / [contact] Email: [contact]	
Evelina Children's Hospital, London [name], Pharmacy Department, Evelina Children's Hospital, [name]. [contact] [contact] Email: [contact]	Royal Manchester Children's Hospital [name] Royal Manchester Children's Hospital Central Manchester Foundation Trust Clinical Trials Room 4th Floor In-Patient Pharmacy Dept [name] [contact] [contact] Email: [contact]
Alder Hey Hospital [name] Pharmacy Department Alder Hey Children's NHS Foundation Trust (Alder Hey) [name] [contact] [contact] Email: [contact]	Derbyshire Children's Hospital [name] Derbyshire Hospitals NHS Foundation Trust [name] [contact] [contact] Email: [contact]
University College London Hospitals [name] Pharmacy Department University College Hospital [name] [contact] [name] [contact] Email: [contact]	Nottingham City Hospital [name] Nottingham University Hospitals NHS Trust Nottingham City Hospital Campus [name] [contact] [contact] Email: [contact]
John Radcliffe Hospital [name] Pharmacy dept, Level 2 John Radcliffe Hospital [name] [contact] [contact] Email: [contact]	Southmead Hospital, Bristol [name] Pharmacy Department Southmead Hospital, [name] [contact] [contact] Email: [contact]

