7.4 Preparation, Dosage and Administration of Study Treatment/s

7.4.1 Dispensing

For each patient treatment will continue for a maximum period of 12 weeks. Upon randomisation patients will be allocated a treatment pack, which will be retained in the pharmacy department and dispensed as detailed below (see also Fig 2 and Appendix I). Each individual treatment pack will comprise:

- 0.5mg – 12 blister packs, each providing 7 days treatment
- 2mg – 11 blister packs, each providing 7 days treatment
- 6mg – 10 blister packs, each providing 7 days treatment
- 12mg – 9 blister packs, each providing 7 days treatment

When pharmacy dispenses the trial treatments they will add their own local dispensing label, which will include the name and address of the hospital, the patient's name, the date of dispensing and instructions for use.

During the 4-week dose increasing phase, trial treatments will be dispensed in volumes sufficient to provide 14 days treatment (2 blister packs) to allow for unplanned delays in review visits.

Week T0

2 blister packs (14 days supply) of 0.5mg dispensed to family by the RP.

Week T+1

Prior to performing the home visit, 1 blister pack of 0.5mg along with 2 blister packs of 2mg (to provide a total of 14 days supply of each) will be dispensed to the Research Practitioner (RP). During the home visit the RP will evaluate the effectiveness of the treatment dose supplied at T0W in accordance with the dose modification criteria (section 7.9.1) and will either issue an additional blister pack of 0.5mg if this dose is to continue for a further week, or increase the dose and supply 2 blister packs of 2mg for the next week of treatment plus an additional pack.

All unused medication (including omitted doses from the previous week's regimen) will be collected by the RP and returned to pharmacy where they will be retained for destruction by PENN at study completion.

Week T+2

The RP will collect 1 week's supply of trial treatment at the patients current dose level, i.e. the same dose level as was prescribed at the T+1W home visit, in addition to 2 weeks supply of the next scheduled dose increase and 2 weeks supply of the previous dose (if applicable).

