The child will be seen again in clinic a minimum of 4 weeks after registration and, if still fulfilling eligibility criteria, will be randomised into the study. The sleep hygiene period can be extended to a maximum of 6 weeks if required to allow flexibility in the scheduling of the randomisation clinic visit. Randomisation will require additional fully informed written consent and assent (if appropriate) (Section 11.3).

The trial duration for each participant is 12 weeks from date of randomisation and it is intended that all randomised patients will receive trial medication throughout their participation. At randomisation each patient will be allocated their own 'individual patient package' containing either melatonin or placebo. These packages will be retained in the pharmacy department of the relevant institution and issued on a weekly basis dependent upon dose to be administered. The child will be given the first dose and kept on that dose for a minimum of seven days. For the next three weeks and at each one-week interval during this time, the child's sleep disorder will be reviewed by the RP during home visits and the medication either left unchanged, increased to the next dose increment based upon the protocol dose modification criteria (see section 7.9.1) or decreased due to the presence of adverse events (see section 7.9.2). The decision to increase medication will be based upon the protocol dose modification criteria: (i) absence of Serious Adverse Events; (ii) a minimum of 5 of 7 days completed in the sleep diary; (iii) no significant increase in seizure activity (where applicable); (iv) child having received at least 5 of the possible 7 doses in the current week; (v) a) child not falling asleep within one hour of 'lights off' or 'snuggling down to sleep' at age-appropriate times for the child in three nights out of five, and/or b) child having less than 6 hours of continuous sleep in three nights out of five.

There are a maximum of 3 dose increments after the starting dose of 0.5 mg, through 2.0mg, 6.0mg and up to a maximum of 12.0mg. After seven days, the child will either be maintained on that dose if the sleep disorder has improved (i.e. the fifth dose modification criteria is no

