11.3.2.2 Prior to Randomisation

The consent process at T0W must be carried out by a medically qualified member of the research team identified in the signature and delegation log. Discussion of objectives, risks and inconveniences of the trial and the conditions under which it is to be conducted are to be provided to patients by staff with experience with minors. Both parental consent and, if appropriate, the patients assent should be obtained **prior** to any study related procedure being carried out.

All patients undertaking the four week sleep hygiene interval, and their parent/legal representative, will have received an appropriate version of the IEC-approved written information prior to consenting to enter the sleep hygiene intervention period. At the next clinic visit following completion of the sleep hygiene intervention, individuals will be re-screened to consider eligibility to enter the treatment phase of the MENDS trial. The investigator will reiterate previous written and verbal explanations about the research study to the patient and their parent/legal representative and answer any questions that may arise.

The patient and their parent/legal representative will have had the opportunity to discuss the study with their surrogates and think about it prior to agreeing to participate. Both the clinician taking consent and the parent/legal representative of the patient must personally sign and date the form.

If capable, the patient should assent and sign and personally date a separate IEC-approved assent form, describing (in simplified terms) the details of the trial intervention/product, trial procedures and risks. The parent or legal representative should also sign and date the assent form. Assent forms do not substitute for the consent form signed by the patient's legally acceptable representative. Where the child is unable to provide assent, this should be documented in the patient's medical notes, and recorded on the age and stage of development specific PISC.

The original copy of the signed consent/assent forms will be retained in the child's medical notes and must be made available for inspection. A copy will be returned to the MCRN CTU and one will also be put in the investigator site file. A further copy of the signed consent/assent forms will be given to the child's parent/legal representative (Appendix B).

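### The pregnancy exclusion is dated to the T-4W visit, when no drug is given, and nothing listed at T0W asks about pregnancy before the first capsules are issued 4 to 6 weeks later

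*Protocol*

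**What the plan says.** Exclusion 8 in Protocol section 5.2 covers "Girls or young women who are pregnant at the time of screening", followed by the label T-4W in brackets. Section 6.1, item 7 of the T-4W list, provides the only pregnancy test tied to a visit: "Pregnancy test for sexually active pubertal females who have consented to this procedure". Families at T-4W agree only to registration, the sleep hygiene period and its assessments (section 8.2).

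Randomisation follows at least 4 weeks after registration, and section 8.1 adds that "The sleep hygiene period can be extended to a maximum of 6 weeks if required". Study drug first appears at Week T0 in section 7.4.1: "2 blister packs (14 days supply) of 0.5mg dispensed to family by the RP".

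The T0W list in section 6.2 has four items: diary and actigraphy compliance, severity of the sleep problem, "A check that they have not been prescribed melatonin since screening", and "Verification that eligibility criteria continue to be fulfilled". Table 2 shows eligibility assessment, medical history review and a complete physical examination at T0, but has no pregnancy row.

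Section 11.1 makes pregnancy an exclusion on safety grounds, citing a theoretical risk of melatonin use in pregnancy. It asks that sexually active girls be counselled and offered a test, names no visit for this, and lets a girl who declines the test enter. Section 10.9.1 stops study drug for a pregnancy that occurs during the study.

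**The concern.** The exclusion exists to avoid exposing a pregnancy to the drug, yet it is fixed to a visit where no exposure takes place. At the visit where exposure starts, the protocol lists no question about pregnancy and no repeat of the test offer. A girl who conceives during the run-in, or whose pregnancy was too early to detect at T-4W, could be randomised and dosed until someone notices. Read literally, a conception during the run-in does not even breach exclusion 8. What is at stake is participant and fetal safety, and agreement between the eligibility wording and the protocol's own stated reason for it. No efficacy estimate depends on it.

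**Working it through.** The plan states no figure to reproduce. The check sets the provisions side by side and adds simple date arithmetic.

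**Timing**

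| Quantity | Source | Result |
|---|---|---|
| Shortest gap, listed test to first issue of drug | section 8.1, 4 weeks | 4 × 7 = 28 days |
| Longest gap | section 8.1, 6 weeks | 6 × 7 = 42 days |
| Drug handed over at T0W | section 7.4.1, 2 packs of 7 | 2 × 7 = 14 days' supply |
| Treatment ceiling | section 7.4.1, 12 weeks | 12 × 7 = 84 days |

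The 84 days apply only if the pregnancy is never recognised, because section 10.9.1 ends dosing on discovery. Two doses are omitted around the T+10W saliva collection (section 8.6.3.1), so the ceiling is 84 − 2 = 82 dosing days.

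**Does the T0W re-check carry exclusion 8 forward?**

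1. Section 6.2 item 4 asks for "Verification that eligibility criteria continue to be fulfilled". Exclusion 8 describes status at T-4W. A girl who was not pregnant then still satisfies it as worded, whatever has happened since.
2. The T0W checks in section 6.2 are themselves called screening, but exclusion 8 adds the T-4W label and so selects the earlier visit.
3. The protocol dates a criterion to T0W when it intends to: inclusion 8, on diary completion, does so.
4. Within section 5.2, only exclusions 1 and 8 are worded by reference to screening. Exclusion 1 is "Children treated with melatonin within 5 months prior to screening", and section 6.2 item 3 brings it up to date by name: "A check that they have not been prescribed melatonin since screening". Exclusion 8 has no matching line.

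**Does anything else at T0W name pregnancy?** The history review, physical examination and eligibility row in Table 2 do not. Section 11.3.2.2 states that "The consent process at T0W must be carried out by a medically qualified member of the research team" and requires the risks to be discussed, but does not mention pregnancy. The counselling and test offer in section 11.1 carry no visit. Section 10.9.1 acts only once a pregnancy is known.

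**Which cases are left?** A girl already pregnant at T-4W is excluded once that is recognised. A known run-in pregnancy would probably be kept off drug under sections 11.1 and 10.9.1, despite the wording of exclusion 8. That leaves the pregnancy unrecognised at T0W, whether conceived in the run-in or too early to detect at T-4W.

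**The case against.** The strongest reply is that the protocol, read as a whole, does re-screen. Section 11.3.2.2 provides for eligibility to be considered again before the treatment phase. Sections 8.1 and 8.2 make randomisation conditional on the child still meeting the criteria, and section 11.1 classes pregnancy as an exclusion without dating it. The duty to counsel and offer a test could be met at T0W. On that reading a known pregnancy would be caught. This is probably right for a known pregnancy, but none of these provisions prompts anyone to look for an unknown one.

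A second reply is that other requirements are dated to screening, such as age and sleep history, and that several exclusions (beta-blockers, sedatives, sleep apnoea) are not named in section 6.2 either. That is true, and item 3 may be there to protect the sleep baseline, so the contrast with exclusion 1 does not prove an oversight. But beta-blockers and sedatives are excluded on current use and sleep apnoea is not tied to T-4W, so a general re-check at T0W can catch them. It cannot do so for exclusion 8.

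A third reply is that section 11.1 is a reasoned choice: little need for testing is expected, the risk is theoretical, and testing is not compulsory. The proposal leaves that choice intact. It remains true that rewording alone detects nothing, that voluntary testing guarantees nothing at any visit, and that a conception just after T0W is not addressed. The information and consent forms and the T0W eCRF were not available for this review, and a pregnancy question could sit there.

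**Conclusion.** The point holds as a low-priority safety correction. Exclusion 8 is tied to a visit 28 to 42 days before drug is first issued, and the visible T0W procedures contain no pregnancy enquiry.

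The numbers concerned are very small. The upper age is 15 years 8 months at screening, and section 11.1 expects few patients, if any, to need a test. Allocation is equal, so about half of any such girls would receive placebo. Exposure would run from T0W until discovery. The conclusion rests on the literal wording of exclusion 8 and on the text of sections 5.2, 6.1, 6.2 and Table 2. It has no bearing on sample size or on the efficacy analysis.

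**What to change.** Reword exclusion 8 so that it applies to girls or young women pregnant at screening (T-4W) or at randomisation (T0W). Keep the T-4W test offer. In the T0W list of section 6.2, next to item 3, add a pregnancy enquiry and a repeat of the voluntary test offer for sexually active pubertal girls, to be completed before drug is dispensed. Leave section 11.1 as it stands, so that declining the test does not prevent entry.

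The enquiry and test offer do the practical work; the rewording makes a positive answer a clear ground for exclusion. The cost is one phrase, one line, one extra question at an existing clinic visit and an occasional voluntary test in very few girls.
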